4.2 Hypotheses

The primary hypothesis is that KPd will improve **ORR by** evaluating whether the lower bound of the 90% CI of the **ORR** excludes **60%**. The secondary hypothesis is that KPd will improve **MRD[-]CR rate at 12 months by** evaluating whether the lower bound of the 90% CI of **the MRD[-]CR rate at 12 months** excludes **3%**. The secondary hypothesis

will be assessed only after the primary objective is met. **Both** exact binomial 2-sided 90% and 95% CIs will be generated **around the point estimate for each of these endpoints.**

5. Study Design

5.1 Overall Design

The study is an open-label, phase 2 trial to assess efficacy and safety of carfilzomib, pomalidomide, and dexamethasone (KPd).

Eligible subjects will have relapsed or relapsed and refractory multiple myeloma after receiving 1 or 2 prior treatment regimens. Subjects must be refractory to lenalidomide and may have been previously exposed to an anti-CD38 antibody therapy. Subject is considered refractory if any of the following criteria is met:

- The best response reached during at least 1 regimen containing the drug of interest was stable disease or progressive disease
- The reason that the drug of interest was stopped was progression in at least 1 regimen
- The date of relapse/progression is after start date and within 60 days after stop date of the drug of interest in at least 1 regimen

According to Protocol Amendment 3, Approximately 85 subjects will be enrolled, with approximately one-third of subjects in the first relapse and two-thirds of subjects in second relapse. **In late 2021, enrollment was discontinued after 54 subjects were enrolled.** Subjects may receive treatment until progression. The regimens will be administered per Section 7.1.

All subjects will be assessed for multiple myeloma disease response according to the International Myeloma Working Group Uniform Response Criteria (IMWG-URC) (Section 12.11) every 28 ± 7 days from cycle 1 day 1 through death, confirmed PD, lost to follow-up, withdrawal of full consent (whichever occurs first), or end of study, regardless of cycle duration, dose delays or treatment discontinuation. Subjects who end study drug(s) before confirmed progressive disease (PD) are required to complete disease response assessments and report new antimyeloma treatment every 28 ± 7 days until first subsequent antimyeloma treatment, death, loss to follow-up, withdrawal of full consent, confirmed progress disease (PD), or end of study, whichever occurs first.

The individual subject disease response and disease progression for this study will be independently assessed by an Independent Review Committee (IRC) in accordance with

the IMWG-URC. The membership criteria and operational details of the IRC will be described in the IRC Charter. The IRC will centrally review the disease-related tests and assessments to evaluate disease progressions and responses without the knowledge of the investigator's disease assessments. The IRC assessment will be used for the analysis of the ORR.

Bone marrow aspirates will be collected as clinically indicated to confirm a response of complete response (CR) or stringent complete response (sCR). Subjects with a suspected CR or better will have a bone marrow for MRD assessment at 12 months \pm 4 weeks unless a minimal residual disease (MRD) assessment was performed within 4 months prior to the scheduled assessment (eg, coordinated with a bone marrow procedure to confirm CR). Subjects with a MRD[-]CR at the first time point (8 to 12 months from initiation of treatment) should have the subsequent MRD assessment 12 months \pm 4 weeks after the earlier assessment (20-24 months after the start of treatment), if subjects have not relapsed nor started new antimyeloma therapy prior to this subsequent MRD assessment.

Subjects who discontinue either carfilzomib or pomalidomide, but not both drugs, will be considered to remain on study treatment.

Safety laboratory studies (complete blood counts and differential, complete metabolic panel) will be collected on day 1 of each cycle, prior to dosing. A Data Review Team (DRT) will convene regularly to independently evaluate safety. Timing and frequency of the DRT meetings will be detailed in the DRT charter. After discontinuation of study treatment, a safety follow-up visit will be scheduled 30 (+3) days after the last dose of study treatment. Subjects who discontinue treatment and either start new antimyeloma treatment or have PD, will enter long-term follow-up every 12 weeks until death or end of study.

The overall study design is described by a study schema in Section 2.1. The endpoints are defined in Section 4.1.

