The study is an open-label, phase 2 trial. Subjects may receive treatment until progression. Myeloma disease status will be monitored locally for response and progression per International Myeloma Working Group (IMWG) criteria (Kumar et al, 2016) every 28 ± 7 days from cycle 1 day 1 until confirmed progressive disease (PD), death, lost to follow-up, or withdrawal of full consent (whichever occurs first), regardless of cycle duration, dose delays or treatment discontinuation. Subjects with a suspected CR or better will have a bone marrow for minimal residual disease (MRD) assessment at 12 and 24 months (\pm 4 weeks) from start of treatment (unless a MRD assessment was performed within 4 months before planned assessment). Subjects who end study drug(s) without confirmed PD are required to complete disease response assessments and report new antimyeloma treatment every 28 ± 7 days until first subsequent antimyeloma treatment, death, lost to follow-up, withdrawal of full consent, confirmed PD, or end of study, whichever occurs first. Subjects who discontinue treatment and either start new antimyeloma treatment or have PD, will enter long-term follow-up every 12 weeks until death or end of study.

Number of Subjects

According to Protocol Amendment 3, approximately 85 subjects will be enrolled in the study, with approximately one-third of subjects in first relapse and two-thirds in second relapse. **In late 2021, enrollment was discontinued after 54 subjects were enrolled.**

Summary of Subject Eligibility Criteria

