4.1 Objectives and Endpoints

Objectives	Endpoints
Primary	

 Estimate the overall response rate (ORR) 	
 objective response defined as the best overall confirmed response of partial response (PR), very good partial response (VGPR), complete response (CR), or stringent complete response (sCR) by Independent Review Committee (IRC) per International Myeloma Working Group Uniform Response Criteria (IMWG-URC)
Key Secondary	

 Estimate the rate of minimal residual disease negative complete response (MRD[-]CR) at 12 months landmark 	
 MRD[-]CR at a sensitivity of 10^{-5} using next generation sequencing (NGS)-based method in the bone marrow at 12 months \pm 4 weeks from start of treatment
Secondary	

 Describe the safety and tolerability of carfilzomib combined with dexamethasone and pomalidomide 	
 subject incidence of treatment-emergent adverse events

 Estimate the frequency of best MRD[-] response in KPd 	
 MRD[-] response at a sensitivity of 10^{-5} using NGS-based method in the bone marrow at any time during therapy

 Estimate the frequency of sustained MRD[-]CR 	
 sustained MRD[-]CR at a sensitivity of 10^{-5} using NGS-based method in the bone marrow defined as subjects that maintain MRD[-]CR 12 months or more after achieving MRD[-]CR status, disregarding when the first MRD[-]CR was reached

 Estimate the frequency of sustained MRD[-]CR at landmark 24 months 	
 sustained MRD[-]CR at a sensitivity of 10^{-5} using NGS-based method in the bone marrow at 24 months \pm 4 weeks from start of treatment and calculated only within the subjects who reached MRD[-]CR in the time window for key secondary endpoint assessment

Objectives	Endpoints

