9.2.2.2 Bone Marrow Sample Evaluation Including FISH and MRD[-]CR Assessment

A baseline bone marrow aspirate sample will be collected at screening, or prior to dosing at cycle 1 day 1. A bone marrow sample obtained as standard of care may be used as the baseline sample if taken within 45 days prior to enrollment for FISH and MRD testing. The first sample obtained for baseline bone marrow aspirate will be for tumor specific sequence identification for MRD measurement by next-generation sequencing (NGS) at the central lab.

After screening, bone marrow aspirate will be obtained:

- at time of suspected CR or better. Depending on when this procedure occurs, an additional aliquot of bone marrow aspirate will be frozen and saved at the central lab for MRD testing to be performed at a later time.
- at time of MRD assessment. MRD will be conducted in subjects with suspected CR or better at 12 months (\pm 4 weeks) but may be performed as early as 8 months after start of treatment in subjects with suspected CR or better. Subjects with a MRD[-]CR response at the first time point should have the subsequent MRD assessment 12 months \pm 4 weeks after the earlier assessment, if subjects have not relapsed nor started new antimyeloma therapy prior to this subsequent MRD assessment.

If the bone marrow aspirate sample taken is found to be of insufficient quantity or quality for testing, the site may be contacted to request provision of a suitable archival bone marrow aspirate sample.

9.2.2.3 Bone Lesion Assessment (Skeletal Survey, Computed Tomography [CT], or Positron Emission Tomography/CT [PET/CT])

Skeletal survey will include lateral radiograph of the skull, anteroposterior and lateral views of the spine, and anteroposterior views of the pelvis, ribs, femora, and humeri. Low-dose whole body computed tomography or fluorodeoxyglucose-positron emission tomography/computed tomography (FDG-PET/CT) may be used in place of skeletal survey. Bone lesion assessment at screening (all subjects) may be done within 28 days prior to enrollment, if performed as a part of standard of care. It should be repeated if worsening clinical symptoms suggest PD or as clinically indicated. The same method of

assessment used at baseline will be used throughout the study. These imaging studies will be read locally.

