- **Date Decision Was Made to End Investigational Product on End of Investigational Product Administration (Carfilzomib), Date Decision Was Made to End Non-Investigational Product on End of Non-Investigational, Product Administration (Dexamethasone), End of Investigational Product Administration (Pomalidomide) and End of Non-Investigational Product Administration (Pomalidomide) CRFs, where the Primary Reason for ending treatment is not Death or Lost to follow-up**

MRD[-]ICR

MRD[-]ICR is defined as achievement of CR (including sCR) per IMWG-URC and MRD[-] status at a sensitivity of 10^{-5} using next generation sequencing (NGS) based method in the bone marrow at any time.

MRD[-]ICR Rate at 12 Months Landmark

MRD[-]CR rate at 12 months landmark is defined as proportion of subjects who reach MRD[-]CR at 12 months landmark assessment among all subjects who received at least 1 dose of carfilzomib. **The sensitivity analysis of MRD[-]CR Rate at 12 months landmark will be based on MRD Evaluable Analysis Set.** The data will include the MRD results from bone marrow samples obtained from subjects with Suspected CR or better obtained no earlier than 8 months and no later than 12 months plus 4 weeks after the start of any study treatment.

MRD[-] Rate at Any Time During Therapy

MRD[-] rate at any time during therapy is defined as proportion of subjects who reach MRD[-] at any time during therapy among all subjects who received at least 1 dose of carfilzomib. **The sensitivity analysis of MRD[-]CR Rate at any time during therapy will be based on MRD Evaluable Analysis Set.** The data will include the MRD results from bone marrow samples obtained from the subjects with a response of VGPR or better at any time during therapy.

Number of cycles started for any study drug

It is defined as the total number of treatment cycles in which at least one dose of any study drug is administered.

Number of cycles started for each study drug

It is defined as the total number of treatment cycles in which at least one dose of carfilzomib/pomalidomide/dexamethasone, respectively, is administered.

Number of cycles started for all study drugs

It is defined as the total number of treatment cycles in which at least one dose of carfilzomib, one dose of pomalidomide and one dose of dexamethasone is administered.

Number of doses of carfilzomib administered

It is defined as the total number of non-zero doses of carfilzomib a subject received during the treatment period of the study

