It will be calculated as the planned cumulative dose of pomalidomide in mg divided by the planned number of weeks for the treatment per protocol based on the corresponding cycle and day of the last pomalidomide infusion. Per protocol, one cycle is 28 days (4 weeks), so the planned number of treatment weeks will be calculated as $4 \times (c-1) + j$, where c is the cycle in which the last pomalidomide dose is taken and $j=1$ if the last pomalidomide dose is taken on day 1 to 7 within the last cycle, $j=2$ if the last dose is given on day 8 to 14, $j=4$ if the last dose is given on day 15 to 21. The planned cumulative dose of pomalidomide is the summation of planned pomalidomide dose (mg) per week ($[7 \times 4, 7 \times 4, 7 \times 4, 0]$) across the planned treatment weeks.

Revised International Staging System (R-ISS) Stage at Baseline

R-ISS stage at baseline will be calculated using ISS, risk group by FISH, and LDH, based on the criteria published by the International Myeloma Working Group ([Palumbo, 2015](#)):

Stage I: ISS stage I and standard risk group by FISH and normal LDH

Stage II: Not R-ISS stage I or III

Stage III: ISS stage III and {either high-risk group by FISH or high LDH}

Sustained MRD[-]CR Rate

Sustained MRD[-]CR rate is defined as the proportion of subjects that maintain MRD[-]CR for 12 months +/- 4 weeks or more, ie, maintaining MRD[-]CR for at least 12 months minus 4 weeks is considered as sustained, after achieving MRD[-]CR status among the subjects who reach the MRD[-]CR status, disregarding when the first MRD[-]CR was reached.

Sustained MRD[-]CR Rate at 24 months

Sustained MRD[-]CR rate at 24 months is defined as the proportion of subjects that maintain MRD[-]CR for 12 months +/- 4 weeks or more, ie, maintaining MRD[-]CR for at least 12 months minus 4 weeks is considered as sustained, after achieving MRD[-]CR status in the time window of **Key Secondary** endpoint assessment.

Time to Response

Time from start of treatment to first date of confirmed PR or better.

Time to Response = (response start date – start of **any study** treatment date + 1) / 30.4

Time (month) since initial diagnosis

Time since initial diagnosis is defined as:

(Date of informed consent signed - date of first diagnosis of MM + 1) / 30.4

Treatment-emergent Adverse Event

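### The 24-month sustained MRD[-]CR endpoint carries a calendar window that the scheduled second marrow can miss, while the analysis sections judge it by the interval since the first MRD[-]CR

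*Protocol*

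**What the plan says.** The documents time this one endpoint in three ways.

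- **Calendar window.** Protocol 4.1 (repeated in the Synopsis and SAP 2.1) asks for MRD[-]CR in a window centred on month 24. Its tolerance, anchor and denominator read: "4 weeks from start of treatment and calculated only within the subjects who reached MRD[-]CR in the time window for key secondary endpoint assessment". SAP Table 9-2, SAP 9.5.2 and the heading in Protocol 10.4.2.2 carry a 24 months ± 4 weeks label, but do not say what it is counted from.
- **Sampling schedule.** Protocol 5.1 refers to subjects with MRD[-]CR "at the first time point (8 to 12 months from initiation of treatment" and puts their next marrow 12 months ± 4 weeks "after the earlier assessment (20-24 months after the start of treatment". Protocol 9.2.2.2 and the MRD row of the Schedule of Activities give the same spacing. Section 9.2.2.2 makes 12 months ± 4 weeks the usual time of the first sample and month 8 the earliest.
- **Interval rule.** SAP Section 5: "Sustained MRD[-]CR rate at 24 months is defined as the proportion of subjects that maintain MRD[-]CR for 12 months", with a 4-week tolerance, counted from MRD[-]CR in the key secondary window. Protocol 10.4.2.2 also counts at least 12 months minus 4 weeks as sustained.

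A further sampling text stands in the Synopsis and SAP 3.1. Of subjects thought to have reached at least CR, it says that they "will have a bone marrow for minimal residual disease (MRD) assessment at 12 and 24 months". Those months count from the first dose with a 4-week tolerance, and the marrow is waived when MRD was assessed in the preceding 4 months. The biomarker row of the Schedule of Activities and Protocol 9.2.9 also speak of 12- and 24-month assessments.

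**The concern.** The calendar window and the marrow schedule are anchored differently: one counts from start of treatment, the other from the first MRD sample. A site that follows Protocol 5.1 exactly can produce a second sample that the objectives tables do not recognise, although the interval rule does.

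Nothing settles which rule prevails. SAP 8.3 says missing outcomes are not imputed. It does not say whether a subject without an in-window sample counts as not sustained or leaves the denominator. The same data could thus yield different sustained rates, with the choice open until the analysis is run.

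**Working it through.** **Inputs**

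| Quantity | Value | Source |
|---|---|---|
| Endpoint window | 24 months ± 4 weeks from start of treatment | Protocol 4.1, SAP 2.1 |
| First sample | 8 to 12 months; data accepted to 12 months + 4 weeks | Protocol 5.1; SAP Section 5 |
| Gap to second sample | 12 months ± 4 weeks | Protocol 5.1, 9.2.2.2, Schedule of Activities |
| Days per month | 30.4 | SAP Section 5 formulas |

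**1. The plan's own range.** 8 + 12 = 20 and 12 + 12 = 24, which reproduces the 20-24 months in Protocol 5.1.

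**2. The endpoint window.** 4 weeks = 28/30.4 = 0.92 month, so the window is 24 − 0.92 = 23.08 to 24 + 0.92 = 24.92 months.

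**3. Overlap with the nominal range.** (24 − 23.08)/4 = 0.23. Only the last 23% of the 20-24 month range lies in the window; 77% lies before it.

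**4. First-sample times that can work.** With an exact 12-month gap, the first sample must fall at 23.08 − 12 = 11.08 to 24.92 − 12 = 12.92 months. If the second visit uses its full + 4 weeks, the first can be as early as 11.08 − 0.92 = 10.16 months, and no earlier. A first sample at month 8 gives a second at 19.08 to 20.92 months, always before the window. A first sample at 12.92 months can give a second as late as 12.92 + 12 + 0.92 = 25.84 months, after it.

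**5. Share of second samples outside the window.** The documents do not give the timing of first samples, so each row is an assumption.

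| Assumed first samples | Exact 12-month gap | Second visit uniform within ± 4 weeks |
|---|---|---|
| All at 12 months ± 4 weeks (uniform) | 0% | about 25% |
| Uniform, 8 to 12.92 months | about 63% | about 67% |
| Uniform, 8 to 12 months | about 77% | about 77% |
| All before about month 10.2 | 100% | 100% |

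**6. One subject under two rules.** MRD[-]CR at months 9 and 21:
- Interval rule: 21 − 9 = 12, which is at least 12 − 0.92 = 11.08, so sustained.
- Calendar rule: 21 is below 23.08, so no in-window sample.

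**7. Size of the denominator.** At the planning rates of 10% and 12% in Protocol Table 10-1, 52 subjects give 52 × 0.10 = 5.2 and 52 × 0.12 = 6.2 subjects with MRD[-]CR at 12 months. With six, reclassifying one subject moves the rate by 1/6, about 17 percentage points.

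**The case against.** The best defence is that the statistical sections already apply a workable rule. Protocol 10.4.2.2 and SAP Section 5 both count the month-9/month-21 subject as sustained, so an analyst working from them loses no one. The Synopsis and SAP 3.1 waive a planned marrow when MRD was assessed in the previous 4 months, so a month-21 sample can stand in for the 24-month one. The 12-month landmark is built in the same way: it is labelled ± 4 weeks, yet SAP Section 5 takes samples "no earlier than 8 months and no later than 12 months plus 4 weeks after the start of any study treatment". Early sampling is also an allowance rather than the default.

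Much of this stands. It rules out a reading that a reader might infer from the 20-24 month range, namely that most second samples will miss the window. That depends on how many first samples are taken early, which the documents do not say; under the default timing all or about three quarters fall inside.

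It does not remove the conflict. The 4-month exception decides whether a marrow is needed; it does not widen the endpoint window. For the 12-month landmark the wider data window is written out. For month 24 it is not, and the objectives tables still state a window that the interval rule does not use.

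**Conclusion.** The inconsistency is real. The objectives tables, applied to the plan's own schedule, leave some correctly timed second samples outside the endpoint window, and all of them when the first sample precedes about month 10.2. The share affected is unknown: 0% or about 25% under default timing, about 77% if first samples are uniform over months 8 to 12.

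A reader might go further and infer that the reported sustained rate will be biased downward. That would need the calendar window to override the interval rule in both statistical sections, and out-of-window subjects to be counted as failures. The documents state neither.

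The endpoint is secondary and descriptive, with confidence intervals but no hypothesis, and lies outside the fixed sequence. The ORR test and the 12-month MRD[-]CR test are untouched. The point still deserves correction because the denominator is expected to be about six (assuming the 12% planning rate holds), so one or two reclassified subjects change the estimate materially.

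**What to change.** Settle one rule before the sustained MRD analysis (Protocol 10.4.1.2, SAP 7.2), so that the choice is not made with results in view.

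- In the Synopsis, Protocol 4.1 and SAP 2.1, replace the calendar window with the interval rule already in Protocol 10.4.2.2 and SAP Section 5: MRD[-]CR maintained for at least 12 months minus 4 weeks after the first MRD[-]CR in the key secondary window.
- Change the 24 months ± 4 weeks labels in Protocol 10.4.2.2, SAP Table 9-2 and SAP 9.5.2 to match.
- Reconcile the 12- and 24-month sampling text in the Synopsis, SAP 3.1, the biomarker row of the Schedule of Activities and Protocol 9.2.9 with Protocol 5.1, 9.2.2.2 and the MRD row of the Schedule.

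Writing out a wider 24-month data window would also work and would keep the landmark. To hold every sample the schedule allows, it would have to run from 19.1 to 25.8 months.

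The cost is protocol and SAP wording; the interval rule needs no additional marrow samples.

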5.2 Number of Subjects

Subjects in this clinical investigation shall be referred to as "subjects". **According to Protocol Amendment 3**, approximately 85 subjects will be enrolled in the study, with approximately one-third of subjects in first relapse and two-thirds of subjects in second relapse. **In late 2021, enrollment was discontinued after 54 subjects were enrolled.**

For the sample size justification, see Section 10.1.

5.2.1 Replacement of Subjects

Subjects who are withdrawn or removed from treatment or the study will not be replaced.

5.2.2 Number of Sites

Approximately 45 investigative sites globally will be included in the study. Sites that do not enroll subjects within 6 months of site initiation may be closed.

